This is an optional sub-study evaluating immunogenicity to vaccine antigens following Tdap administration in participants with moderate-to-severe AD participating in study B7451036.

Up to approximately 90 eligible participants may enroll in this sub-study. The sub-study participants will remain in their treatment groups as previously randomized in the main study; up to approximately 30 participants of each treatment groups will be enrolled. Study participants are required to provide a separate informed consent (with consent by the legal guardian and assent by the adolescent, as appropriate). All eligible participants participating in the sub-study must continue with all study assessments of the main study per the Schedule of Activities.

The sub-study schedule is integrated into Visits 7 and 8 of the main study.

PARTICIPANT SELECTION

The following eligibility criteria are designed to select participants for whom participation in the sub-study is considered appropriate. All relevant medical and non-medical conditions should be taken into consideration when deciding whether this sub-study is suitable for a particular participant.

Sub-Study Inclusion Criteria

Participant eligibility should be reviewed and documented by an appropriately qualified member of the investigator's study team before participants are included in the sub-study. Participants need to maintain eligibility in the B7451036 main study. In addition, participants must meet all of the following inclusion criteria to be eligible for enrollment into the sub-study:

1. Participants are expected to continue participation in the main study from Weeks 8 to 12 as scheduled;
2. No safety issues, eg clinically significant thrombocytopenia from laboratory testing at Week 4 of the main study, and no other safety concerns at Week 8 of the main study;
3. Evidence of a personally signed and dated informed consent document indicating that the participant and his/her parent(s)/legal guardian, if applicable, has been informed of all pertinent aspects of the sub-study. A separate informed consent and assent, if applicable (from the main study consent/assent) is required. (see Appendix 10.1.3 for informed consent process);
4. Participants who are willing and able to comply with scheduled sub-study, procedures.

Participants presenting with any of the following will not be included in the study:

1. Received any prior tetanus, diphtheria or pertussis vaccine within the last 5 years of Visit 7.

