- Sub-study baseline visit (Visit 7 [Week 8] in main study): Pre-vaccination blood samples will be collected for measurement of concentrations of IgG against various vaccine antigens. A single dose of Tdap vaccine will then be administered.
- Sub-study follow-up visit (Visit 8 in main study): Blood samples will be collected 4 weeks post-vaccination at Visit 8 (Week 12 of the main study) for measurement of concentrations of IgG against various vaccine antigens.

ASSESSMENTS

Continue assessments described in the main study Schedule of Activities.

ADVERSE EVENT REPORTING

See Section 8.3 and Appendix 3 of the main study.

DATA ANALYSIS/STATISTICAL METHODS

Data analysis for the immunogenicity sub-study will be carried out when all enrolled participants have completed or have withdrawn from this sub-study. Results from this analysis are considered final for the sub-study.

Methodologies for summary and statistical analyses of data collected in this sub-study are summarized here and further detailed in a statistical analysis plan (SAP), which will be dated and maintained by Pfizer.

The SAP may modify what is outlined in the protocol; however, any major modifications of the endpoint definitions or their analyses will also be reflected in a protocol amendment.

Sample Size Determination

With 30 participants per arm, there is about 80% power to detect a ratio of geometric mean concentrations (GMCs) (at 4 weeks post-vaccination) between PF-04956842 200 mg QD and placebo of up to 23% (which means the GMC for 200 mg QD is at least 77% lower than the GMC for placebo). The Type-I error is set at 5%.

This sample size also provides a 95% confidence interval for the ratio of GMCs with an upper limit of ~3.15 times the estimated ratio with 95% chance.

Under an assumption of no difference, there is approximately 81% chance to rule out ratios (of GMCs 200 mg QD relative to placebo) of less than 0.64.

Similar statements apply to the 100 mg QD versus placebo comparison.

Analysis of Immunogenicity Endpoints

The primary immunogenicity analysis will be descriptive in nature; there will be no formal hypothesis testing, though 95% two-sided confidence intervals will be formed.

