6.3. Other Endpoint(s)

6.3.1. Immunogenicity Sub-Study

- Endpoints:
 - Fold Increase from Baseline in Concentrations of IgG Against Tetanus Toxoid, Diphtheria Toxoid, Pertussis Toxoid, Pertactin (PRN), Filamentous Hemagglutinin (FHA), and Fimbriae Types 2 and 3 (FIM) at 4 Weeks Post vaccination.
- Analysis set: Immunogenicity sub-study Analysis Set (Section 4).
- Analysis methodology: CI using the Student's t distribution in Section 5.2.2 for the geometric mean fold rise (GMFR).
- Intercurrent events and missing data: Only observed data will be used.
- The number, median, first and third quartiles, minimum, maximum for the fold increase will be presented for each treatment arm.
- GMFR and the responding 95% CI will be presented for each treatment arm.
- GMFR ratio and the responding 95% CI between treatment groups for each PF-04965842 dose group versus placebo will also be presented.

CCI

[Redacted]

[Redacted]

[Redacted]

[Redacted]

[Redacted]

[Redacted]

[Redacted]

[Redacted]

[Redacted]

[Redacted]

090177e19618b8f5\Approved\Approved On: 25-Jan-2021 08:47 (GMT)

CC
I [REDACTED]

CCI [REDACTED]

I [REDACTED]

I [REDACTED]

I [REDACTED]

I [REDACTED]

I [REDACTED]

I [REDACTED]

I [REDACTED]

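### Tdap sub-study: the stated 81% chance to rule out GMC ratios below 0.64 is only about 13–14% on the protocol's own figures

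*Protocol*

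**What the plan says.** The Sample Size Determination text in Protocol Appendix 11 (Section 10.11) makes three statements for 200 mg QD against placebo with 30 per arm:

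1. About 80% power, with a Type-I error of 5%, to detect a ratio of post-vaccination geometric mean concentrations (GMCs) of up to 23%, "which means the GMC for 200 mg QD is at least 77% lower than the GMC for placebo".
2. A "95% confidence interval for the ratio of GMCs with an upper limit of ~3.15 times the estimated ratio with 95% chance".
3. If there is no true difference, "there is approximately 81% chance to rule out ratios (of GMCs 200 mg QD relative to placebo) of less than 0.64".

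It adds: "Similar statements apply to the 100 mg QD versus placebo comparison". No SD is given, and nothing indicates that the third statement uses a different SD or confidence level from the first two.

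On the analysis, the appendix says that "there will be no formal hypothesis testing, though 95% two-sided confidence intervals will be formed", on log-transformed concentrations. Enrolment is described as "up to approximately 30 participants of each treatment groups will be enrolled". SAP Section 6.3.1 plans this output: "GMFR ratio and the responding 95% CI between treatment groups for each PF-04965842 dose group versus placebo will also be presented". The sample-size text in SAP Section 2.2 covers only the main study, so it neither repeats nor corrects these statements.

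**The concern.** Power to detect a ratio and the chance to exclude that ratio when there is no effect are, for the same design and interval, the same quantity. A design with about 80% power only at a 77% reduction cannot also have an 81% chance of excluding a 36% reduction.

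The sub-study is meant to show whether vaccination during treatment impairs the response to Tdap, and the protocol expects its findings to extend to other vaccines. With no hypothesis test planned, interval precision is what the sub-study delivers. Read as written, the third statement says that, absent an effect, losses above 36% would very probably be excluded.

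**Working it through.** **Inputs.** From Appendix 11: n = 30 per arm; ratios 0.23 and 0.64; factor 3.15 with 95% assurance; Type-I error 5%, taken here as two-sided to match the planned intervals. Assumed: common SD in both arms, all 30 evaluable, unadjusted comparison on the log10 scale with Student's t. Then df = 58, t(0.975, 58) = 2.002, √(2/30) = 0.2582, log10 0.23 = −0.6383, log10 3.15 = 0.4983, log10 0.64 = −0.1938.

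**Step 1: the contradiction without an SD.** Let SE = SD × √(2/30). When the true ratio is 1, the chance that the 95% interval lies wholly above r is P(T > 2.002), where T is non-central t with non-centrality |log10 r| / SE. Power to detect r has the same critical value and non-centrality, apart from a negligible wrong-direction tail. So 80% power at 0.23 is an 80% chance to exclude 0.23, and an 81% chance to exclude 0.64 would be 81% power for a 36% reduction.

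**Step 2: SD implied by statement 1.** Normal approximation: 0.6383 / [0.2582 × (1.960 + 0.842)] = 0.882. Non-central t: 0.868.

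**Step 3: SD implied by statement 2.** The factor is 10^(t × SE × √(χ²(0.95, 58)/58)), where the last root is 1.1505. So SD = 0.4983 / (2.002 × 0.2582 × 1.1505) = 0.838. This SD gives 83% power at 0.23, so statements 1 and 2 agree.

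**Step 4: statement 3 at those SDs, true ratio 1.**

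| Quantity | SD 0.868 | SD 0.838 |
|---|---|---|
| SE | 0.2240 | 0.2164 |
| Non-centrality, 0.1938 / SE | 0.865 | 0.896 |
| Chance that the two-sided 95% interval excludes 0.64 | 13.4% | 14.0% |
| Same, one-sided 5% limit | 21.5% | 22.4% |
| Chance that the two-sided 95% interval excludes 0.23 | 80.0% | 82.7% |
| Chance that the point estimate exceeds 0.64 | 80.7% | 81.5% |
| Ratio excluded with 81% chance | 0.226 | 0.237 |

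Simulation of 200,000 trials at each SD gives 13.3% and 14.0% for the third row.

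**Step 5: what would make 81% true.** At 30 per arm, a log10 SD of 0.26. The upper-limit factor would then be 1.43 instead of 3.15, and power at 0.23 would exceed 99.9%. At the implied SDs, about 300 to 335 per arm would be needed.

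**Step 6: possible sources of the sentence.** Two explanations fit, and the documents do not decide between them:

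- 81% is the chance that the point estimate exceeds 0.64 (sixth row). That excludes nothing below 0.64. The interval half-width is a factor of 2.81 or 2.71, so an observed 0.64 carries an interval from 0.64/2.81 = 0.228 to 0.64 × 2.81 = 1.80, or from 0.236 to 1.73.
- 0.64 is |log10 0.23| = 0.638, not back-transformed. The intended ratio would then be 0.23 (fifth row).

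Under either explanation, the ratio that the interval excludes with about 81% chance is about 0.23.

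**The case against.** The best defence is that the numbers are sound and only the verb is wrong: read as the chance that the estimate exceeds 0.64, the sentence fits the paragraph's own SD. That may well be the origin. But ruling out is a statement about the interval, and the sentence fails on that reading.

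A second defence is that the sub-study is optional and descriptive, that no margin or success criterion uses 0.64, and that the same paragraph openly gives the two unfavourable figures. This stands as to consequence: no conclusion is tied to the sentence. It does not make the sentence right.

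Third, 13–14% rests on rounded inputs (about 80%, about 3.15) and on reading the 5% as two-sided, which the protocol does not say. A one-sided reading of statement 1 gives a larger SD and about 11%. That is a fair caution about the second digit, and it moves further from 81%.

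Fourth, an unstated SD or a baseline adjustment might have been intended. None is mentioned, and adjustment would have to remove about 90% of the variance to reach 81%.

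Finally, all three statements concern post-vaccination GMC, whereas SAP Section 6.3.1 reports the ratio of geometric mean fold rises. This stands as a limit: no SD for the fold rise is given, so its precision cannot be derived from the documents.

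**Conclusion.** The concern holds. As worded, the third statement is wrong: the planned interval would exclude 0.64 in about 13–14% of trials, against 81% stated. At these SDs the observed ratio would have to reach 1.73 to 1.80 (0.64 × 2.71 to 0.64 × 2.81) to do so. No confidence-limit reading tried comes near 81%. Because 30 per arm is approximately the upper limit, precision may be lower: the chance is about 12% at 25 per arm and 10–11% at 20.

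The contradiction needs no SD. The size of the correction rests on the assumptions listed with the inputs, and applies to post-vaccination GMC only. The co-primary analyses and the main-study error rate are unaffected.

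**What to change.** State the assumed SD, its log base, and the quantity to which the precision statement applies, including whether it is the GMC ratio or the fold-rise ratio in the SAP. Recompute from that SD, then use one of these:

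- keep 81% and give the ratio as about 0.23, a reduction of more than about 77%;
- keep 0.64 and give the chance as about 13–14%;
- if the point estimate was meant, give 81% as the chance that the observed ratio exceeds 0.64, and drop the words about ruling out.

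Carry the change to the 100 mg comparison. Add that, on these planning assumptions, finding no difference would not exclude a substantial reduction.

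The cost is one corrected sentence, a stated SD and a less favourable precision claim. Data collection, endpoints and analysis do not change.

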10.12. Appendix 12: Peak Pruritus NRS

Protocol ID: _____

CENTER				SUBJECT ID										
DATE														
		-				-								
dd			MMM					yyyy						

PEAK PRURITUS NRS

Language administered: (44) English for USA

On a scale of 0 to 10, with 0 being 'no itch' and 10 being 'worst itch imaginable', how would you rate your itch at the worst moment during the previous 24 hours?

0	1	2	3	4	5	6	7	8	9	10
No itch										Worst itch imaginable

©Regeneron Pharmaceuticals, Inc. and Sanofi (2017)

090177e19618b8f7\Approved\Approved On: 25-Jan-2021 08:51 (GMT)

10.13. Appendix 13: Frequency of Pruritus NRS

Frequency of Pruritus

Select the number that best describes frequency of itching due to Atopic Dermatitis over the past 24 hours (check one number only).

										
0	1	2	3	4	5	6	7	8	9	10
Never /No itching									Always/constant itching	

CCI [Redacted]

[Redacted]

[Redacted]

CCI [Redacted]

10.15. Appendix 15: Patient Global Assessment (PtGA)

Overall, how would you describe your Atopic Dermatitis right now?

Choose only ONE response.

- Severe
- Moderate
- Mild
- Almost Clear
- Clear

10.16. Appendix 16: European Quality of Life 5 Dimension Youth Scale (EQ-5D-Y)

Describing your health TODAY

Under each heading, please check the ONE box that best describes your health TODAY.

Mobility (walking around)

I have no problems walking around

I have some problems walking around

I have a lot of problems walking around

Taking care of myself

I have no problems taking a bath or shower by myself or getting dressed by myself

I have some problems taking a bath or shower by myself or getting dressed by myself

I have a lot of problems taking a bath or shower by myself or getting dressed by myself

Doing usual activities (for example, going to school, hobbies, sports, playing, doing things with family or friends)

I have no problems doing my usual activities

I have some problems doing my usual activities

I have a lot of problems doing my usual activities

Having pain or discomfort

I have no pain or discomfort

I have some pain or discomfort

I have a lot of pain or discomfort

Feeling worried, sad, or unhappy

I am not worried, sad, or unhappy

I am a little worried, sad, or unhappy

[figure not shown]
I am very worried, sad, or unhappy

090177e19618b8f7\Approved\Approved On: 25-Jan-2021 08:51 (GMT)

How good is your health TODAY

- We would like to know how good or bad your health is TODAY.
- This line is numbered from 0 to 100.
- 100 means the best health you can imagine.
- 0 means the worst health you can imagine.
- Please mark an X on the scale to indicate how your health is TODAY.

The best health
you can imagine

[figure not shown]
The worst health
you can imagine

090177e19618b8f7\Approved\Approved On: 25-Jan-2021 08:51 (GMT)

10.17. Appendix 17: Children's Dermatology Life Quality Index (CDLQI)

CHILDREN'S DERMATOLOGY LIFE QUALITY INDEX

The aim of this questionnaire is to measure how much your skin problem has affected you OVER THE LAST WEEK. Please tick ✓ one box for each question.

- | | | | | |
|-----|---|--|--|---|
| 1. | Over the last week, how itchy , " scratchy ", sore or painful has your skin been? | Very much
Quite a lot
Only a little
Not at all | 

 | |
| 2. | Over the last week, how embarrassed or self conscious , upset or sad have you been because of your skin? | Very much
Quite a lot
Only a little
Not at all | 

 | |
| 3. | Over the last week, how much has your skin affected your friendships ? | Very much
Quite a lot
Only a little
Not at all | 

 | |
| 4. | Over the last week, how much have you changed or worn different or special clothes/shoes because of your skin? | Very much
Quite a lot
Only a little
Not at all | 

 | |
| 5. | Over the last week, how much has your skin trouble affected going out , playing , or doing hobbies ? | Very much
Quite a lot
Only a little
Not at all | 

 | |
| 6. | Over the last week, how much have you avoided swimming or other sports because of your skin trouble? | Very much
Quite a lot
Only a little
Not at all | 

 | |
| 7. | 
Last week, was it school time? 
 
OR
 
was it holiday time? 
 | 
If school time: Over the last week, how much did your skin problem affect your school work?
 
If holiday time: How much over the last week, has your skin problem interfered with your enjoyment of the holiday?
 | 
Prevented school
Very much
Quite a lot
Only a little
Not at all
 
Very much
Quite a lot
Only a little
Not at all
 | 

 



 |
| 8. | Over the last week, how much trouble have you had because of your skin with other people calling you names , teasing , bullying , asking questions or avoiding you ? | Very much
Quite a lot
Only a little
Not at all | 

 | |
| 9. | Over the last week, how much has your sleep been affected by your skin problem? | Very much
Quite a lot
Only a little
Not at all | 

 | |
| 10. | Over the last week, how much of a problem has the treatment for your skin been? | Very much
Quite a lot
Only a little
Not at all | 

 | |

Please check that you have answered EVERY question. Thank you.

©M.S. Lewis-Jones, A.Y. Finlay, May 1993, This must not be copied without the permission of the authors.

090177e19618b8f7\Approved\Approved On: 25-Jan-2021 08:51 (GMT)

10.18. Appendix 18: Patient Oriented Eczema Measure (POEM)

POEM for self-completion

Please circle one response for each of the seven questions below about your eczema. Please leave blank any questions you feel unable to answer.

- 1. Over the last week, on how many days has your skin been itchy because of your eczema?
No days 1-2 days 3-4 days 5-6 days Every day
- 2. Over the last week, on how many nights has your sleep been disturbed because of your eczema?
No days 1-2 days 3-4 days 5-6 days Every day
- 3. Over the last week, on how many days has your skin been bleeding because of your eczema?
No days 1-2 days 3-4 days 5-6 days Every day
- 4. Over the last week, on how many days has your skin been weeping or oozing clear fluid because of your eczema?
No days 1-2 days 3-4 days 5-6 days Every day
- 5. Over the last week, on how many days has your skin been cracked because of your eczema?
No days 1-2 days 3-4 days 5-6 days Every day
- 6. Over the last week, on how many days has your skin been flaking off because of your eczema?
No days 1-2 days 3-4 days 5-6 days Every day
- 7. Over the last week, on how many days has your skin felt dry or rough because of your eczema?
No days 1-2 days 3-4 days 5-6 days Every day

Total POEM Score (Maximum 28):

© The University of Nottingham

090177e19618b8f7\Approved\Approved On: 25-Jan-2021 08:51 (GMT)

10.19. Appendix 19: Hospital Anxiety and Depression Scale (HADS)

HOSPITAL ANXIETY AND DEPRESSION SCALE:

(Page 1 of 2)

Clinicians are aware that emotions play an important part in most illnesses. If your clinician knows about these feelings he or she will be able to help you more.

This questionnaire is designed to help your clinician to know how you feel. Read each item below and **check the reply** which comes closest to how you have been feeling in the past week. Ignore the numbers printed next to the replies.

Don't take too long over your replies, your immediate reaction to each item will probably be more accurate than a long, thought out-response.


1. I feel tense or 'wound up'
 
 3 Most of the time
 
 2 A lot of the time
 
 1 From time to time, occasionally
 
 0 Not at all
 
2. I still enjoy the things I used to enjoy
 
 0 Definitely as much
 
 1 Not quite so much
 
 2 Only a little
 
 3 Hardly at all
 
3. I get a sort of frightened feeling as if something awful is about to happen
 
 3 Very definitely and quite badly
 
 2 Yes but not too badly
 
 1 A little, but it doesn't worry me
 
 0 Not at all
 
4. I can laugh and see the funny side of things
 
 0 As much as I always could
 
 1 Not quite so much now
 
 2 Definitely not so much now
 
 3 Not at all
	
5. Worrying thoughts go through my mind
 
 3 A great deal of the time
 
 2 A lot of the time
 
 1 Not too often
 
 0 Very little
 
6. I feel cheerful
 
 3 Never
 
 2 Not often
 
 1 Sometimes
 
 0 Most of the time
 
7. I can sit at ease and feel relaxed
 
 0 Definitely
 
 1 Usually
 
 2 Not often
 
 3 Not at all
 
8. I feel as if I am slowed down
 
 3 Nearly all of the time
 
 2 Very often
 
 1 Sometimes
 
 0 Not at all

--	--

HADS copyright © R.P. Snaith and A.S. Zigmond, 1983, 1992, 1994. Record form items originally published in Acta Psychiatrica Scandinavica, 67, 361-70, copyright © Munksgaard International Publishers Ltd, Copenhagen 1983. This edition first published in 1994 by nferNelson Publishing Company Ltd., 414 Chiswick High Road, London W4 5TF. GL Assessment is part of the Granada Group.

090177e19618b8f7\Approved\Approved On: 25-Jan-2021 08:51 (GMT)

HOSPITAL ANXIETY AND DEPRESSION SCALE:

(Page 2 of 2)

9. I get a sort of frightened feeling like 'butterflies' in the stomach

- 0 Not at all
- 1 Occasionally
- 2 Quite often
- 3 Very often

10. I have lost interest in my appearance

- 3 Definitely
- 2 I don't take as much care as I should
- 1 I may not take quite as much care
- 0 I take just as much care as ever

11. I feel restless as if I have to be on the move

- 3 Very much indeed
- 2 Quite a lot
- 1 Not very much
- 0 Not at all

12. I look forward with enjoyment to things

- 0 As much as I ever did
- 1 Rather less than I used to
- 2 Definitely less than I used to
- 3 Hardly at all

13. I get sudden feelings of panic

- 3 Very often indeed
- 2 Quite often
- 1 Not very often
- 0 Not at all

14. I can enjoy a good book or radio or television program

- 0 Often
- 1 Sometimes
- 2 Not often
- 3 Very seldom

Now check that you have answered all the questions

HADS copyright © R.P. Snaith and A.S. Zigmond, 1983, 1992, 1994. Record form items originally published in Acta Psychiatrica Scandinavica, 67, 361-70, copyright © Munksgaard International Publishers Ltd, Copenhagen 1983. This edition first published in 1994 by nferNelson Publishing Company Ltd., 414 Chiswick High Road, London W4 5TF. GL Assessment is part of the Granada Group.

090177e19618b8f7\Approved\Approved On: 25-Jan-2021 08:51 (GMT)

10.20. Appendix 20: Pruritus and Symptoms Assessment for Atopic Dermatitis (PSAAD) Symptom Diary

Pruritus and Symptoms Assessment for Atopic Dermatitis (PSAAD)

Please answer each question by thinking about your skin condition (most often called atopic eczema or atopic dermatitis) over the past 24 hours. This includes today and last night.

For each question, think about all the areas of your body affected by your skin condition and choose the number that best describes your experience.

1) How itchy was your skin over the past 24 hours?

0	1	2	3	4	5	6	7	8	9	10
Not itchy										Extremely itchy

2) How painful was your skin over the past 24 hours?

0	1	2	3	4	5	6	7	8	9	10
Not painful										Extremely painful

3) How dry was your skin over the past 24 hours?

0	1	2	3	4	5	6	7	8	9	10
Not dry										Extremely dry

4) How flaky was your skin over the past 24 hours?

0	1	2	3	4	5	6	7	8	9	10
Not flaky										Extremely flaky

5) How cracked was your skin over the past 24 hours?

0	1	2	3	4	5	6	7	8	9	10
Not cracked										Extremely cracked

6) How bumpy was your skin over the past 24 hours?

0	1	2	3	4	5	6	7	8	9	10
Not bumpy										Extremely bumpy

7) How red was your skin over the past 24 hours?

0	1	2	3	4	5	6	7	8	9	10
Not red										Extremely red

8) How discolored (darker or lighter) was your skin over the past 24 hours?

0	1	2	3	4	5	6	7	8	9	10
Not discolored										Extremely discolored

9) How much did your skin bleed over the past 24 hours?

0	1	2	3	4	5	6	7	8	9	10
No bleeding										Extreme bleeding

10) How much did your skin seep or ooze fluid (other than blood) over the past 24 hours?

0	1	2	3	4	5	6	7	8	9	10
No seeping or oozing										Extreme seeping or oozing

11) How swollen was your skin over the past 24 hours?

0	1	2	3	4	5	6	7	8	9	10
Not swollen										Extremely swollen

Sleep & Usual Activities Questions

12) How much did your skin condition make it difficult for you to sleep over the past 24 hours?

0	1	2	3	4	5	6	7	8	9	10
No difficulty sleeping										Could not sleep at all

13) How much did your skin condition make it difficult for you to do your usual activities over the past 24 hours?

0	1	2	3	4	5	6	7	8	9	10
No difficulty doing usual activities										Could not do usual activities at all

**Patient Global Impression of Severity (PGIS) & Patient Global
Impression of Change Questions (PGIC) Questions**

14) Please rate the severity of your skin condition right now:

- Not present
- Very mild
- Mild
- Moderate
- Moderately Severe
- Severe
- Extremely Severe

15) Compared to the beginning of the study, how would you describe the severity of your skin condition today?

- Much better
- Better
- A little better
- No change
- A little worse
- Worse
- Much worse

